## 1.0 Objectives / Specific Aims

The goal of this project is to establish the safety, feasibility, and acceptability of abbreviating and accelerating telehealth-delivered imaginal exposure therapy for post-traumatic stress disorder (PTSD). Importantly, conventional telehealth-delivered Prolonged Exposure (PE) therapy is non-inferior to the conventional, gold standard in-person PE for PTSD (Acierno et al., 2017). Intensive or massed schedules of in-person exposure- based trauma-focused treatments have likewise recently been shown, in a nascent but promising literature, to produce comparable treatment outcomes to conventional once or twice weekly schedules, but importantly, with lower levels of premature dropout (Sciarrino et al., 2020; Zoellner et al., 2017).

**AIM 1: Establish the safety of VVC-delivered massed imaginal exposure for PTSD.** We hypothesize that VVC-delivered, massed imaginal exposure will be safe as indexed by no significant adverse events.

**AIM 2: Establish the feasibility, tolerability, and acceptability of VVC-delivered massed imaginal exposure for PTSD.** We hypothesize that 1) veterans will consider the treatment acceptable and tolerable and that 2) recruitment and retention will be feasible (> 80% retention).

**EXPLORATORY AIM 1: Establish acceptability among stakeholder providers of VVC-delivered massed imaginal exposure for PTSD.** We hypothesize that 1) telemental healthcare providers will consider the treatment acceptable and tolerable and that 2) will be willing to receive training and/or refer patients to such services.

**EXPLORATORY AIM 2: Establish the preliminary efficacy of VVC-delivered massed imaginal exposure for PTSD.** We hypothesize that 1) veterans will demonstrate moderate reductions in posttraumatic stress and associated symptoms and impairment from intake to the end of treatment that will in turn, 2) be maintained or extended at the 1-month post-treatment follow-up.

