## 2.0 Background

**The need for enhancing PTSD treatment.** PTSD is a chronic, impairing condition with variable rates of recovery. PE, which consists primarily of imaginal and in vivo forms of exposure to trauma reminders, is an effective first-line intervention (Power et al., 2010), with wide acceptance among evidence-based practitioners. However, many PTSD patients show non- remittance (~25-50%; Rosellini et al., 2018), poor treatment responses (~60%); Loerinc et al., 2015) and dropout (~18-68%; Imel et al. 2013). Thus, there are well-defined needs to improve the efficacy, effectiveness, efficiency, and tolerability of this challenging, but potent form of intervention, and an equally pressing need to develop and deploy technologies that enhance access to treatment.

**Accelerated protocols for enhancing treatment efficacy and efficiency.** In response to calls to enhance the efficiency of exposure-based treatments, accelerated protocols have been demonstrated to be non-inferior to the standard PE protocol. This includes a previous trial by Col [name] and colleagues that implemented a daily 6-session protocol (Zoellner et al., 2017), resulting in comparable efficacy and much lower dropout (6.3%) compared to standard bi-

weekly 10-session PE. This is consistent with a small, but growing number of studies of massed evidence-based treatments for PTSD, which have revealed large effects ( $d = 1.15\text{--}2.93$ ) and low attrition across studies (5.1%; Sciarrino et al., 2020). Thus, by reducing burden by enhancing efficiency, accelerated protocols may especially be indicated for those at high risk of dropout, such as Veterans (28.1%; Eftekhari et al., 2013).

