**Impact and innovation.** The goal of this proposal is in line with the priorities of the VHA and HSR&D priorities as well as the priorities of the Charleston HEROIC RIVR Pilot Project Program. Specifically, this proposal aligns with the mission stipulated in the HEROIC RFA to focus on “novel applications of telemental healthcare delivery including feasibility and/or preliminary efficacy/effectiveness trials”.

We propose that there is strong potential for broader implementation of intensive or massed exposure-based, trauma-focused treatments, and that such implementation could be even greater if virtual deployment is feasible and acceptable to patient and provider alike. Furthermore, an alternative VVC-delivered trauma- focused treatment with shorter demands on total duration

could broaden VA providers' arsenal of evidence- based interventions. This would enable greater tailoring of treatment plans to individual veteran preferences for frequency and duration of sessions as well as more flexible accommodation to daily life demands and related scheduling barriers. Taken together, we propose that establishing the safety, feasibility, and acceptability of massed exposure-based therapy delivered via VA Video Connect is a productive first step toward advancing telemental health treatment options and furthering personalized care for our veterans.

Importantly, in regards to the likelihood of impact from an implementation standpoint, all proposed VVC and therapeutic methods (imaginal exposure) in this proposal are already widely adopted across the VA system. This includes an extensive IT infrastructure for supporting VVC and the nation's largest cadre of evidence- based, trauma-focused therapists. As such, if findings from this pilot and follow up RCTs indicate safety, acceptability and efficacy, VVC-delivered massed trauma-focused therapy could be readily implemented in the VA system.

Our proposal includes unique and important contributions to veteran mental healthcare through the following innovations:

- For the first time, we will establish the safety, feasibility, tolerability, and acceptability of VVC-delivered, massed imaginal exposure for PTSD. While these aspects have been established for in-person imaginal exposure, the remote nature of VVC presents unique challenges.

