- For the first time, we will establish the preliminary efficacy of VVC-delivered, massed imaginal exposure for PTSD. While these findings will be preliminary as the study is not powered for efficacy, it will provide preliminary estimates of pre- to post- effect sizes and variance in outcomes that will aid in planning well-crafted and properly statistically powered follow up RCTs.
- COVID-19 has fundamentally altered the delivery landscape for clinical and research practice. The methods proposed here further advance the VA's capacity to promote evidence-based care and research amidst unforeseen disruptions to in-person procedures.
- For the first time, we will establish acceptability among stakeholder providers, of VVC-delivered, massed imaginal exposure for PTSD. While in-person, massed imaginal exposure has been effective in RCTs, the perceptions of evidence-based clinical providers at the forefront of treating veterans have not been assessed. In order to assess implementation likelihood, as well as to assess the need to disseminate findings and techniques, input from provider stakeholders is essential.

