#### 4.0 Inclusion and Exclusion Criteria/ Study Population

Veterans who are aged 18-65 (inclusive), who meet full DSM-5 criteria for current PTSD will be recruited from all racial, ethnic and gender categories. The rationale regarding a cutoff of 65 years was for correspondence to prior massed in-person protocols (e.g., Zoellner et al, 2017). Planned follow up studies will include a broader age range and will be powered to analyze age effects on outcomes. To contend with dropout, we propose to enroll 25 veterans, with the aim of completing assessments and treatment for 20 participants. In-person investigations have shown a dropout rate of 5% (Sciarrino et al. 2020), thus a 20% allowance will ensure adequate recruitment to meet study aims.

**Exclusion Criteria.** Participants will be excluded for the following: 1. clinically unstable physical illness; 2. bipolar Type I disorder; 3. dementia; 4. repeated abuse or dependence upon drugs within 3 months; 5. unstable psychotropic regimen within 6-weeks; and finally, 6. active suicidal ideation or a suicide attempt within the past year.

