## 10.0 Data Management

**Data Acquisition.** If (and only if) ultimately approved by the VA, we propose the use of VA Qualtrics, which is a secure, FedRAMP-authorized online data capture system that is widely used as a HIPPA-compliant web-based means to collect sensitive research data. Moreover, if approved, in addition to remotely collecting validated self-report questionnaire data from participants using this platform, we also request leveraging Qualtrics' functionality to integrate java script, which would enable us to directly capture audio and visual data from the participant's side from their webcam and microphone. This is an excellent alternative to our initially proposed procedures, which involve collecting streamed, then captured (i.e., on the clinician's side) footage. This is problematic due to significant temporal distortion and low sampling rate for screen-captured footage on currently deployed telehealth platforms approved by the VA (i.e., Teams, Webex, and VVC). As mentioned, the use of Qualtrics will be entirely contingent on obtaining full MUSC IRB and VA R&D approval for our proposed use. If ultimately not approved, we will continue to implement our procedures that involve capturing questionnaire data with hard copies, by mail.

**Data Preparation.** Pre-processing of data as the study progresses will allow for more expedient dissemination of study findings. As appropriate, pre-processing will follow standard best practices to ensure excellent data quality and security. Prior to analyses, data will be visually and statistically inspected for the presence of aberrant data points, which will be omitted prior to analyses.

**Analytical Plan.** Descriptive statistics will be reported for safety, feasibility, tolerability, and acceptability. Linear mixed-effects models will be used to characterize trajectories of change in symptoms and impairment, while controlling for potential confounders, such as baseline severity.

Following standard pre-processing steps, analyses will be conducted using generalized linear models, and will proceed in a bottom-up manner involving selection of the best fitting fixed and random growth terms, followed by adding predictors of interest. Factors (e.g., sex) will be dichotomously coded, whereas all continuous predictors will be scaled and centered as a function of baseline values to allow for meaningful interpretation of effects as indicative of reliable change.

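### Aim 1 would establish safety from no significant adverse events, but 0 of 25 still allows a true rate up to 13.7%; a smaller point is that the planned 20 of 25 completers (80.0%) does not satisfy Aim 2's strict > 80% retention

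*Combined protocol and SAP*

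**What the plan says.** **Safety.** Aim 1 in section 1.0 is to establish the safety of the treatment. Its hypothesis is that "VVC-delivered, massed imaginal exposure will be safe as indexed by no significant adverse events". Under Impact and innovation, section 2.0 repeats the claim: "we will establish the safety, feasibility, tolerability, and acceptability of VVC-delivered, massed imaginal exposure for PTSD". The next part of that list limits the efficacy findings: "While these findings will be preliminary as the study is not powered for efficacy". The Analytical Plan in section 10.0 says: "Descriptive statistics will be reported for safety, feasibility, tolerability, and acceptability". It states no confidence interval, and the documents give no tolerable event rate. Section 2.0 also presents the pilot as a first step and makes wider implementation depend on follow-up RCTs as well as on this study.

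**Retention.** Aim 2 in section 1.0 hypothesizes that "recruitment and retention will be feasible (> 80% retention", a strict inequality. In section 4.0, "we propose to enroll 25 veterans, with the aim of completing assessments and treatment for 20 participants". That section cites 5% dropout from in-person studies and concludes: "thus a 20% allowance will ensure adequate recruitment to meet study aims".

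**The concern.** Aim 1's only stated benchmark is the absence of significant adverse events. In a single arm of 25 people that result is compatible with true rates that few readers would call established safety. Without an interval beside it, 0 of 25 can be read as a stronger finding than it is. The plan states the limit of its sample size for efficacy and leaves it unstated for safety, where the claim is firmer and the same 25 people supply the evidence.

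On retention, two figures that should describe the same target disagree at the boundary. If exactly 20 of 25 complete, the trial meets its section 4.0 completion aim and misses its Aim 2 hypothesis.

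**Working it through.** **Inputs.** N = 25, target completers 20, allowance 20% and cited dropout 5% (section 4.0). Retention criterion > 80% (section 1.0, Aim 2). Dropout 6.3% for the daily six-session protocol and 28.1% for Veterans (section 2.0). Single arm, no control (section 3.0). The documents set no confidence level for safety; 95% is my assumption, and both one-sided and two-sided limits are shown.

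**1. The plan's own figure.** Inflating 20 completers for 20% dropout gives 20 / (1 − 0.20) = 25. The enrolment figure reproduces.

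**2. Upper limit after zero events.** The exact (Clopper-Pearson) limit for 0 of n is 1 − (α/2)^(1/n) two-sided and 1 − α^(1/n) one-sided.

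- n = 25, two-sided 95%: 1 − 0.025^(1/25) = 0.137
- n = 25, one-sided 95%: 1 − 0.05^(1/25) = 0.113
- n = 24, two-sided 95%: 1 − 0.025^(1/24) = 0.142
- n = 23, two-sided 95%: 1 − 0.025^(1/23) = 0.148

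The smaller denominators are relevant because section 9.0 (Treatment Procedures) places treatment after the baseline visit and eligibility determination, within a week. Someone enrolled may therefore never start, and a treatment-safety rate should not count that person.

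**3. How often zero events would be seen anyway.** The documents give no expected rate, so these true rates are illustrative. P(0 of 25) = (1 − p)^25:

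- 2%: 0.98^25 = 0.603
- 5%: 0.95^25 = 0.277
- 10%: 0.90^25 = 0.072

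**4. Retention at the boundary.** 20/25 = 0.800, which is not above 0.80. The smallest passing count is 21/25 = 0.840. With X binomial (n = 25, p = 1 − dropout), P(X = 20) = [25!/(20! 5!)] × p^20 × (1 − p)^5:

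| Dropout | Where it comes from | P(exactly 20) | P(at least 21) | P(at least 20) |
|---|---|---|---|---|
| 5% | section 4.0, in-person | 0.6% | 99.3% | 99.9% |
| 6.3% | section 2.0, daily six-session protocol | 1.4% | 98.2% | 99.6% |
| 20% | section 4.0, full allowance | 19.6% | 42.1% | 61.7% |
| 28.1% | section 2.0, Veterans | 12.7% | 12.8% | 25.5% |

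Section 2.0 does not give the 28.1% as a rate for massed treatment, so the last row is an adverse scenario, not an expectation.

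**5. Precision of the retention estimate.** Two-sided exact 95% intervals are 59.3% to 93.2% for 20/25 and 63.9% to 95.5% for 21/25.

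**The case against.** The best defence is that this is an open-label feasibility pilot and says so. Establish is the verb of every aim, including the one on preliminary efficacy. Aim 1's benchmark is worded as a hypothesis, not as a decision rule. A promise of descriptive statistics does not rule out an interval. Section 2.0 calls the work a first step and wants follow-up RCTs before implementation.

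Much of this stands, and it limits the safety claim in part. It does not remove the point: the explicit statement that findings are preliminary is attached to efficacy alone, and the safety benchmark comes with no measure of its uncertainty.

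Three stronger readings are tempting, and the documents support none of them.

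- A reader might infer that the follow-up RCTs would be planned on a zero-event result. Section 2.0 says their planning will draw on effect sizes and outcome variance, and section 9.0 refers to the efficacy estimate. Neither mentions the adverse-event rate.
- A reader might infer that the sample size was miscalculated or must grow. The enrolment arithmetic is correct, and an estimation aim is compatible with N = 25.
- A reader might infer that the trial plans to miss its own retention hypothesis. The 20 is a cautious planning floor and not a declared success rule: at the cited 5% dropout the expected number retained is 25 × 0.95 = 23.75.

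The opposite claim, that exactly 20 completers is improbable at every cited rate, also fails: at 28.1% it has a probability of 12.7%.

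**Conclusion.** The point holds as one of inference and reporting. Zero significant adverse events in 25 treated participants cannot exclude a true rate up to 13.7% (two-sided exact 95%; 11.3% one-sided), or 14.2% and 14.8% if 24 or 23 start treatment. These are limits of what the data could exclude. They are not expected rates, and they are no evidence that the treatment is unsafe. They assume independent participants and a 95% level.

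The retention mismatch is real but minor. It has a consequence only if exactly 20 complete, with probability 0.6% to 1.4% at the cited rates for massed treatment, 19.6% if dropout equals the full allowance and 12.7% at the Veteran figure. This takes retained to mean completing treatment and assessments among all 25 enrolled, the reading closest to section 4.0.

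Two terms are also undefined. Section 11.0 speaks of serious and non-serious events, and the plan does not say how significant relates to them. Section 9.0 records sessions and visits attended without saying how many make a participant retained. These gaps should be closed, but the conclusion does not depend on them.

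**What to change.** Keep N = 25 and make these changes:

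1. Restate Aim 1 as a preliminary estimate of the adverse-event rate. Report it with a two-sided exact (Clopper-Pearson) 95% interval among participants who start at least one session, and carry the same wording into section 2.0.
2. Report retention among all enrolled with the same type of interval.
3. Make the retention figures agree. Either state the Aim 2 criterion as at least 80%, acknowledging that this loosens it slightly (by the probability of exactly 20 in the table above), or set the completion target at 21 of 25 and the allowance at 4/25 = 16%. Settle this before any retention data are reviewed. That includes the semi-annual internal monitoring committee reviews and the interim analysis at N = 13 (section 11.0).
4. Alongside this, define a significant adverse event and its relation to the section 11.0 categories. Define retained as well: how many of the six sessions, and which of the 1-week and 1-month assessments.

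The cost is protocol wording, two definitions and two intervals. No participants, visits or data are added. The downside is that the stated claims become slightly less favourable.

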## 2.0 Background

**The need for enhancing PTSD treatment.** PTSD is a chronic, impairing condition with variable rates of recovery. PE, which consists primarily of imaginal and in vivo forms of exposure to trauma reminders, is an effective first-line intervention (Power et al., 2010), with wide acceptance among evidence-based practitioners. However, many PTSD patients show non- remittance (~25-50%; Rosellini et al., 2018), poor treatment responses (~60%); Loerinc et al., 2015) and dropout (~18-68%; Imel et al. 2013). Thus, there are well-defined needs to improve the efficacy, effectiveness, efficiency, and tolerability of this challenging, but potent form of intervention, and an equally pressing need to develop and deploy technologies that enhance access to treatment.

**Accelerated protocols for enhancing treatment efficacy and efficiency.** In response to calls to enhance the efficiency of exposure-based treatments, accelerated protocols have been demonstrated to be non-inferior to the standard PE protocol. This includes a previous trial by Col [name] and colleagues that implemented a daily 6-session protocol (Zoellner et al., 2017), resulting in comparable efficacy and much lower dropout (6.3%) compared to standard bi-

weekly 10-session PE. This is consistent with a small, but growing number of studies of massed evidence-based treatments for PTSD, which have revealed large effects ( $d = 1.15\text{--}2.93$ ) and low attrition across studies (5.1%; Sciarrino et al., 2020). Thus, by reducing burden by enhancing efficiency, accelerated protocols may especially be indicated for those at high risk of dropout, such as Veterans (28.1%; Eftekhari et al., 2013).

**Telehealth delivery of exposure-based interventions.** Enhancing access is another critical aspect of improving interventions. The VA system has served as a guidepost for deployment of empirically-supported telehealth interventions for PTSD, and our PTSD Clinical Team (PCT) completed 1,800+ telehealth therapy visits using VA video connect (VVC) in the last year. Further, recent seminal work from Ralph H. Johnson VAMC (RHJVAMC) investigators has demonstrated equivalence of telehealth-delivered versus standard in- person PE for reducing trauma-related symptoms (Acierno et al., 2017). Additionally, Col [name] and colleagues (2020) have recently summarized the emerging literature showing the equivalence of intensive trauma-focused treatment (e.g., daily sessions) in comparison to standard weekly, or bi-weekly protocols (Sciarrino et al., 2020). The present pilot study reflects an extension of these efforts, by evaluating a telehealth- delivered accelerated treatment consisting of the core imaginal exposure component of PE.

**Remote affective and physiological measures.** Theoretical and empirical support suggests emotional and physiological engagement with feared, dreaded, and avoided targets is requisite for therapeutic change to occur in exposure-based interventions (Foa & Kozak, 1986; Lang, 1979). While it is customary in PE to assess engagement based on self-reported distress, there is a need to integrate more objective measures of emotional and physiological activation. For instance, there is relatively low correspondence between subjectively-reported and objectively-measured engagement, and whereas heightened physiological activation predicts better outcomes, blunted physiological activation predicts poorer outcomes in exposure-based treatments ([name] & Tuerk, 2015). Of course, telehealth delivery presents challenges to physiological monitoring. However, recent technological advancements, including in areas of machine learning, afford the ability to monitor physiological activation and other affective markers entirely remotely. This is achieved by extracting affective and physiological signals, such as heart rate, respiratory rate, and facial and vocal affective markers based solely on visual and acoustic features of ordinary webcam footage (e.g., van der Kooij & Naber, 2019).

**Impact and innovation.** The goal of this proposal is in line with the priorities of the VHA and HSR&D priorities as well as the priorities of the Charleston HEROIC RIVR Pilot Project Program. Specifically, this proposal aligns with the mission stipulated in the HEROIC RFA to focus on “novel applications of telemental healthcare delivery including feasibility and/or preliminary efficacy/effectiveness trials”.

We propose that there is strong potential for broader implementation of intensive or massed exposure-based, trauma-focused treatments, and that such implementation could be even greater if virtual deployment is feasible and acceptable to patient and provider alike. Furthermore, an alternative VVC-delivered trauma- focused treatment with shorter demands on total duration

could broaden VA providers' arsenal of evidence- based interventions. This would enable greater tailoring of treatment plans to individual veteran preferences for frequency and duration of sessions as well as more flexible accommodation to daily life demands and related scheduling barriers. Taken together, we propose that establishing the safety, feasibility, and acceptability of massed exposure-based therapy delivered via VA Video Connect is a productive first step toward advancing telemental health treatment options and furthering personalized care for our veterans.

Importantly, in regards to the likelihood of impact from an implementation standpoint, all proposed VVC and therapeutic methods (imaginal exposure) in this proposal are already widely adopted across the VA system. This includes an extensive IT infrastructure for supporting VVC and the nation's largest cadre of evidence- based, trauma-focused therapists. As such, if findings from this pilot and follow up RCTs indicate safety, acceptability and efficacy, VVC-delivered massed trauma-focused therapy could be readily implemented in the VA system.

Our proposal includes unique and important contributions to veteran mental healthcare through the following innovations:

- For the first time, we will establish the safety, feasibility, tolerability, and acceptability of VVC-delivered, massed imaginal exposure for PTSD. While these aspects have been established for in-person imaginal exposure, the remote nature of VVC presents unique challenges.
- For the first time, we will establish the preliminary efficacy of VVC-delivered, massed imaginal exposure for PTSD. While these findings will be preliminary as the study is not powered for efficacy, it will provide preliminary estimates of pre- to post- effect sizes and variance in outcomes that will aid in planning well-crafted and properly statistically powered follow up RCTs.
- COVID-19 has fundamentally altered the delivery landscape for clinical and research practice. The methods proposed here further advance the VA's capacity to promote evidence-based care and research amidst unforeseen disruptions to in-person procedures.
- For the first time, we will establish acceptability among stakeholder providers, of VVC-delivered, massed imaginal exposure for PTSD. While in-person, massed imaginal exposure has been effective in RCTs, the perceptions of evidence-based clinical providers at the forefront of treating veterans have not been assessed. In order to assess implementation likelihood, as well as to assess the need to disseminate findings and techniques, input from provider stakeholders is essential.

